10.4.7 Vital Signs, Electrocardiogram, and Physical Examination

Vital signs and ECG parameters will be listed and presented descriptively, where applicable.

Vital signs include temperature, pulse rate, respiratory rate, and blood pressure (systolic blood pressure and diastolic blood pressure). Vital sign parameters at each timepoint, and change from baseline to worst on study result will be summarised using descriptive summary statistics for each parameter by group. The normal ranges of vital signs are listed in [Appendix 5](#).

The 12-lead ECG data will be summarised by group and listed by patient. ECGs will be judged by the Investigator as clinically significant (yes/no). The number and percentage of subjects with clinically significant ECG findings will be summarised by group for each timepoint. Any abnormal findings in the continuous ECG monitoring will be listed.

Abnormal physical examination findings will be described and listed by group and scheduled timepoint.

10.5 Pharmacokinetic Measurements and Analyses

10.5.1 Drug Concentration Measurements and Analysis

Individual and mean plasma concentrations at each sampling timepoint for rezafungin will be presented by listings and descriptive statistics including: n, mean, standard deviation (SD), standard error (SE), geometric mean, coefficient of variation expressed as percent (CV%), median, minimum and maximum, as well as quartiles (Q1 and Q3).

10.5.2 Pharmacokinetic Parameters

For Parts 1 and 2, the following PK parameters will be determined from the rezafungin concentration-time data using non-compartmental methods (Phoenix WinNonlin®, Build 8.0.0.3176 or higher, Certara USA, Inc., Princeton, New Jersey, US) and actual sampling times:

C_{\max}	Maximum observed plasma concentration
t_{\max}	Time at which the maximum plasma concentration was observed
AUC_{0-t}	Area under the plasma concentration-time curve from time 0 to the time of the last quantifiable concentration
$AUC_{0-\infty}$	Area under the plasma concentration-time curve from time 0 extrapolated to infinity
$t_{1/2}$	Terminal elimination half-life
λ_z	Terminal elimination rate constant
CL	Total clearance
V_{ss}	Volume of distribution at steady-state
V_z	Apparent volume of distribution during the terminal phase

10.5.3 Pharmacokinetic Evaluation

Summary statistics of PK parameters including means, geometric means, medians, ranges, SDs, and CVs around the arithmetic and geometric means will be presented by group.

All PK parameters will be calculated by non-compartmental analysis.

10.6 Interim Analysis

No formal interim analysis is planned for this study.

A DSMB has been appointed for this study. Three interim reviews by the DSMB are planned during this study: one after completion of Part 1, the second review after 50% of data from Groups 2 and 3 (Part 2) are available, and a third interim review after completion of Part 2. For

the third DSMB review, PK and safety data from both Part 1 and Part 2 will be included for review.

Part 1: The first interim review will be performed after completion of Group 1. Review of safety and PK data by the DSMB will be performed after all subjects in Group 1 have completed the Follow-up visit. Recruitment for Group 2 and Group 3 will be started only after DSMB completes the review and confirms the safety. The dose and PK sampling timepoints for Part 2 may be adjusted as appropriate after assessment of the PK and safety data of Part 1.

Part 2: After the review of data from Group 1 by the DSMB and a decision to proceed to Part 2, enrolment in Group 2 and Group 3 will be started in parallel. A second interim review by DSMB is planned when data from 50% of the subjects enrolled in Part 2 are available. The second interim review of the safety and PK data will be performed to ensure that the exposure achieved in subjects from this age group is safe and well tolerated, and inform whether adjustments to the dose and PK sampling timepoints are required for the remaining subjects. Recruitment/dosing in Group 2 and Group 3 will not be paused during DSMB review 2.

Part 3: A third DSMB review will be performed when Part 2 is completed. Enrolment for Group 4 will not start until the juvenile animal toxicity studies are completed, the animal safety data have been reviewed, and the safety and tolerability from the preceding Parts have been confirmed by the DSMB. The dose and sampling time points may be adjusted as appropriate after assessment of the PK and safety data of Part 1 and Part 2.

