A second interim review of safety and PK data will be performed when data from 50% of the subjects enrolled in Part 2 (Group 2 and Group 3) are available. The dose and PK sampling timepoints may be adjusted as appropriate after review of the PK and safety data (DSMB review 2). After completion of Groups 2 and 3; there will be another interim DSMB review (DSMB review 3) of the safety, tolerability, and PK data from the subjects in Groups 1, 2, and 3 (all subjects in Part 1 and Part 2).

A series of juvenile animal toxicity studies will be conducted in parallel with this PK study to investigate the effect of rezafungin on the growing and developing nervous system. Enrolment for Group 4 will not start until the juvenile animal toxicity studies are completed,

Formatte
Color(RG)
Formatte
Custom C
grammar

the animal safety data have been reviewed, and the safety and tolerability from the preceding parts have been confirmed by the DSMB.

Part 3: Subjects from birth to <2 years (Group 4) will be enrolled in Part 3. The planned dose for this age group is 5 mg/kg. Due to blood volume restriction, PK sampling will be done at only 3 timepoints for Group 4: at the end of infusion (\pm 15 minutes), at 24 hours (\pm 4 hours) after start of infusion, and at 168 hours (\pm 12 hours) after start of infusion. A maximum total of 1 mL of blood will be collected for PK sampling. The dose, PK sampling timepoints, extent of safety laboratory data required, and length of the Follow-up period may be adjusted as appropriate after review of the PK and safety data from Part 1 and Part 2 (DSMB review 3).

Investigational Medicinal Product: Rezafungin acetate (MR907)

Rezafungin is a sterile product of lyophilised powder for reconstitution with sterile water for injection prior to dilution into infusion bags containing normal saline, half-normal saline, or 5% dextrose. Each single-dose vial contains rezafungin acetate (200 mg of active rezafungin).

Dose: The dose for Group 1 is 3 mg/kg (not to exceed a total dose of 200 mg). The planned dose for both Group 2 and Group 3 is 4 mg/kg (not to exceed a total dose of 200 mg), and for Group 4, the planned dose is 5 mg/kg. However, the doses for Groups 2, 3, and 4 will be confirmed after a review of the interim PK and safety data from the preceding part(s) by the DSMB (DSMB review 1 and review 3). The dose may be adjusted as appropriate after the review.

Mode of administration: IV infusion over 2 hours (\pm 5 minutes).

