The Safety Analysis Set (i.e., all subjects who have received any amount of rezafungin) will be used for the analysis of safety data.

Safety will be evaluated through treatment-emergent adverse events (TEAEs), serious adverse events (SAEs), adverse events of special interest (AESIs), clinical laboratory, vital signs, electrocardiogram (ECG), and physical examination findings. TEAEs are defined as adverse events (AEs) with an onset on or after administration of the investigational product (IP; rezafungin) until the Follow-up.

Adverse events will be coded using the most recent version of the Medical Dictionary for Regulatory Activities (MedDRA).

The number and percentage of subjects experiencing TEAEs will be summarised by group, severity, and relation to IP. Treatment-emergent adverse events will be summarised by MedDRA System Organ Class and Preferred Term. The number and percentage of subjects reporting at least one TEAE will be summarised for each group (Groups 1, 2, 3, and 4), and overall. All AEs will be listed by subject.

Clinical laboratory data to be summarised include haematology, blood chemistry, and urinalysis. Laboratory data will be converted to International System of Units for reporting and processing purposes. Absolute values and changes from baseline will be presented descriptively. Laboratory data outside the reference ranges will be flagged, and clinical significance of the laboratory value change will be stated. Vital signs and 12-lead ECG data will be summarised by group and listed by subject. The number and percentage of subjects with clinically significant ECG findings will be summarised by group for each time-point. A summary of abnormal physical examination findings by group and scheduled visit (Study day) will be presented.

Interim Analysis

No formal interim analysis is planned for this study.

[figure not shown]
A DSMB has been appointed for this study to monitor the safety. Three interim reviews by the DSMB are planned during the study: The first interim review will be performed after completion of Part 1 (Group 1). The enrolment for Part 2 (Group 2 and Group 3) will commence only after DSMB review of Group 1 data and a decision to go ahead.

A second interim review by the DSMB is planned when data from 50% of the subjects enrolled in Part 2 are available.

[figure not shown]

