A third DSMB review will be performed when Part 2 is completed. Enrolment for Part 3 (Group 4) will not start before review of safety and PK data from Part 1 and Part 2 is complete.

Figure 1 Study Schema

[figure not shown]
Part 1:

Part 2:

Part 3:

DSMB=Data Safety Monitoring Board; IV=intravenous; PK=pharmacokinetic

*Adult formulation; † paediatric formulation; ‡ DSMB review 2 to be held when 50% data from Group 2 and Group 3 are available; # Interim DSMB review 3: Interim review of safety and PK data of all subjects from Part 1 and Part 2 (Groups 1, 2 and 3).

Table 1 Schedule of Assessments for Part 1 (Group 1: 12 to <18 Years) and Part 2 (Group 2: 6 to <12 Years; and Group 3: 2 to <6 Years)

Study Period	Screening	Dosing		PK Sampling Postdose					Follow-up / ET ^a
Study Day	Day -3 to Day -1	Day 1		Day 1			Day 3	Day 8	Day 30 ± 5 Days
Procedure		Predose	Single IV infusion of rezafungin	end-of-infusion ± 15 mins	Between 3 and 4 hrs after start of infusion	Between 6 and 8 hrs after start of infusion	48 hrs ± 4 hrs after start of infusion	168 hrs ± 12 hrs after start of infusion	
Informed consent/assent for minors ^b	x								
Assess inclusion/exclusion criteria	x								
Demography (age, sex, and race)	x								
Baseline characteristics (height, weight, BMI*, and disease characteristics [indication for antifungal prophylaxis/treatment])	x								
Hospitalisation status at Screening (general ward/ICU) ^c	x								
Medical/surgical history and current medical conditions	x								
Prior and concomitant medication use ^d	x	x	x	x	x	x	x	x	x
Physical examination ^e	x	x	x	x	x	x	x	x	x

Study Period	Screening	Dosing		PK Sampling Postdose					Follow-up / ET ^a
Study Day	Day -3 to Day -1	Day 1		Day 1			Day 3	Day 8	Day 30 ± 5 Days
Procedure		Predose	Single IV infusion of rezafungin	end-of-infusion ± 15 mins	Between 3 and 4 hrs after start of infusion	Between 6 and 8 hrs after start of infusion	48 hrs ± 4 hrs after start of infusion	168 hrs ± 12 hrs after start of infusion	
Vital signs (temperature, pulse rate, respiratory rate, and blood pressure) ^f	x	x	x ^f	x ^f	x	x	x	x	x
Clinical laboratory tests (haematology, biochemistry, urinalysis) ^g	x								x
Urine pregnancy test for postmenarchal females	x								x
12-lead ECG ^h	x				x				
IP administration ⁱ			x						
Continuous vital sign and ECG monitoring (only during IP infusion) ^j			x						
PK Sampling (venous or arterial samples) ^k				x	x	x	x	x	
AE/SAE monitoring			x	x	x	x	x	x	x

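### Does DSMB review 2 need a minimum number of subjects from each of Groups 2 and 3?

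*Combined protocol and SAP*

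**What the plan says.** Section 5.1 plans 8 subjects in Group 2 and 8 in Group 3, with up to 2 replacements in each. Section 10.6 says that "enrolment in Group 2 and Group 3 will be started in parallel"; no pacing between the groups is given.

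Review 2 is described in several places:

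- Section 10.6, Part 2 paragraph: "A second interim review by DSMB is planned when data from 50% of the subjects enrolled in Part 2 are available".
- Synopsis, Summary of Study Design: "when data from 50% of the subjects enrolled in Part 2 (Group 2 and Group 3) are available". The synopsis paragraph on interim analysis gives the same rule.
- Section 5.1, Part 2: about half of the subjects aged 2 to <12 years. The fraction is explicitly approximate.
- Section 10.6, opening: "the second review after 50% of data from Groups 2 and 3 (Part 2) are available".
- Figure 1 footnote: "DSMB review 2 to be held when 50% data from Group 2 and Group 3 are available".

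The review is to "inform whether adjustments to the dose and PK sampling timepoints are required for the remaining subjects". Section 10.6 adds: "Recruitment/dosing in Group 2 and Group 3 will not be paused during DSMB review 2". The synopsis fixes the number of looks: "Three interim reviews by the DSMB are planned during the study". The third follows completion of Part 2. Section 10.5.3 has PK parameters summarised by group.

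**The concern.** A count over both groups can be met by very different mixes. With 8 subjects needed and 8 places in each group, the rule allows any split from 4:4 to 8:0. The footnote to Figure 1 and the opening of Section 10.6 could also be read as half of each group, so two readers might call the review at different times.

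The purpose of the review makes the split matter. If the first 8 divide 6:2, then 6 of the 8 planned subjects still to come belong to the group with only 2 observed. Review 3 comes too late for any Part 2 subject. The pause and stop rules in Section 8.1 respond mainly to adverse events and outside data, not to measured exposure. On this view, a dose or sampling decision for one age group could rest largely on children from the other.

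**Working it through.** The protocol states no subject count for review 2 and no precision target (Section 10.1 says that no formal sample size calculation was made), so there is no figure of its own to reproduce. Planned Part 2 size is 8 + 8 = 16, and half is 8. If all replacement places are used, it is 20 and 10.

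**Split of the first 8.** Let k be the number from Group 3.

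- Random order of the 16: P(k) = C(8,k)·C(8,8−k)/C(16,8), with C(16,8) = 12870. P(k ≤ 2) = (1 + 64 + 784)/12870 = 0.066. For either group, 2 × 849/12870 = 0.132.
- Independent arrivals at equal rates: Binomial(8, 1/2). P(k ≤ 2) = (1 + 8 + 28)/256 = 0.145. For either group, 0.289.
- Unequal arrivals: Binomial(8, p), where p is the assumed share of the faster group.

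Chance that the smaller contribution is at or below a given number:

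| Accrual (assumed) | 0 | ≤ 1 | ≤ 2 |
|---|---|---|---|
| Random order | 0.0002 | 0.010 | 0.132 |
| Equal rates | 0.008 | 0.070 | 0.289 |
| 60:40 | 0.017 | 0.115 | 0.365 |
| 70:30 | 0.058 | 0.257 | 0.563 |
| 80:20 | 0.168 | 0.503 | 0.798 |

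At equal accrual both groups therefore supply at least 3 subjects in 87% (1 − 0.132) or 71% (1 − 0.289) of cases.

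**What a small group can show.** The 95% limits for a geometric mean are the estimate multiplied and divided by exp(t·s/√n), where s = √ln(1 + CV²). Between-subject CV is not given. At an assumed 30%, s = 0.294:

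- n = 2: 0.07 to 14
- n = 3: 0.48 to 2.07
- n = 4: 0.63 to 1.60
- n = 8: 0.78 to 1.28

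Two subjects say almost nothing about their own group, and four still leave a wide interval.

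**Alternative A: a separate look for each group at 4 of its 8.** The first look comes when one group reaches 4, with j = 0 to 3 from the other.

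- Equal rates: P(j) = 2·C(3+j,3)/2^(4+j) = 0.125, 0.25, 0.3125, 0.3125. Mean total is 4 + 1.81 = 5.81, and P(j ≤ 2) = 0.69.
- Random order: P(j) = 2·C(3+j,3)·C(12−j,4)/12870 = (990, 2640, 4200, 5040)/12870. Mean total is 6.03, and P(j ≤ 2) = 0.61.

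The first look at the shared dose then has about 6 subjects, and the second group usually has 2 or fewer at that look. Its own look comes later, possibly as a fourth meeting.

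**Alternative B: one look, once both groups have 4.** The total is 8 to 12. The mean is 9.08 in random order and 9.80 at equal rates (each group capped at 8). Subjects still to be dosed then average 16 − 9.08 = 6.9 or 16 − 9.80 = 6.2, against 8 under the planned rule, before counting those dosed while the review is under way.

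**The case for a change.** The best case for a change is that the protocol itself expects age to matter. It plans different mg/kg doses for 12 to <18, 2 to <12 and under 2 years (Section 5.3). It names body surface area as a covariate of exposure while dosing by weight. Section 5.2 says that paediatric PK usually cannot be predicted precisely from adults. Groups 2 and 3 are defined, filled and summarised separately. On that view, whether the older half of the band speaks for the younger half is something review 2 should test. Part 2 needs a substantial amendment anyway, so new wording would cost little, and the DSMB charter is mentioned only for the board's composition.

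Part of this stands. The trigger is worded in more than one way, its count is not stated, and the point at which data become available is not tied to Day 8 PK or Day 30 Follow-up, whereas review 1 waits for completed Follow-up visits.

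The stronger claim does not stand. The same Section 5.3 gives Groups 2 and 3 one planned mg/kg dose and one cap, and Sections 5.1 and 10.6 describe the review as a check on a single age group. Section 5.2 plans a population model from these data, in which children from one half of the band inform the other. The review informs a judgement; it forces no adjustment on a group with two observations. The approximate fraction in Section 5.1 leaves room to wait for another subject or two.

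**Conclusion.** The observation is accurate, but no change follows. Four statements of the trigger count Part 2 subjects together. Of the two looser ones, the opening of Section 10.6 names Part 2 as the unit and is followed in the same section by the explicit rule, and the other is a figure footnote. Analysts would reasonably take the trigger as about 8 of 16 and show the board the data by group, as Section 10.5.3 already does for PK parameters.

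Counting the groups together is a fair trade-off. The risk accepted is a 13% to 29% chance at equal accrual that one group has 2 or fewer subjects, and more if accrual is uneven. That rests on assumed accrual and on a cut-off of 2 chosen for illustration; at 1 or fewer it is 1% to 7%. In return, the shared dose is examined once, on about 8 subjects, within three planned reviews. Separate looks bring the first one to about 6 subjects, and a requirement of 4 in each group delays it to 9 or 10 on average with dosing not paused. Neither alternative is clearly better, and 4 of 8 has no precision basis in the plan. No hypothesis is tested (Section 10.2), so no error rate depends on the split.

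Using one wording and naming the count and data cut in the Part 2 amendment would be sensible housekeeping. The DSMB charter was not available and may already settle these details.

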10.7 Population PK Modelling

The PK data from all groups may also be analysed using nonlinear mixed-effects modelling. Any PK modelling will be subject to a separate analysis plan and will be reported separately from the clinical study report for this study.

11 APPENDICES FOR SUPPORTING DOCUMENTATION AND OPERATIONAL CONSIDERATIONS

Appendix 1: Regulatory, Ethical, and Study Oversight Considerations

Regulatory and Ethical Considerations

This study will be conducted in accordance with the CSP and in accordance with the following:

- Consensus ethical principles derived from international guidelines including the Declaration of Helsinki and Council for International Organisations of Medical Sciences (CIOMS) international ethical guidelines.
- Applicable ICH GCP guidelines.
- Applicable local laws and regulations.

The CSP, protocol amendments, ICF, IB, and other relevant documents (e.g., advertisements) will be submitted to an IEC by the Investigator for review and approval prior to the eligibility screening.

Any amendments to the CSP will require IEC approval before implementation of changes made to the study design, except for changes necessary to eliminate an immediate hazard to study subjects.

CSPs and any substantial amendments to the CSP will require health authority approval prior to initiation except for changes necessary to eliminate an immediate hazard to study subjects.

The Investigator will be responsible for the following:

- Providing written summaries of the status of the study to the IEC annually or more frequently in accordance with the requirements, policies, and procedures established by the IEC.
- Notifying the IEC of SAEs or other significant safety findings as required by IEC procedures.
- Providing oversight of the conduct of the study at the site and adherence to requirements of Code of Federal Regulations Title 21 (21 CFR), ICH guidelines, the IEC, European regulation 536/2014 for clinical studies (if applicable), and all other applicable local regulations.

Financial Disclosure

Investigators and sub-investigators will provide the Sponsor with sufficient, accurate financial information as requested to allow the Sponsor to submit complete and accurate financial certification or disclosure statements to the appropriate regulatory authorities. Investigators are responsible for providing information on financial interests during the course of the study and for 1 year after completion of the study.

Informed Consent Process

Informed consent and assent should be obtained by means of a Subject/Patient Information Sheet and ICF, prepared in accordance with ICH E6 and applicable local regulations, written in

non-technical, age-appropriate language. The Investigator or his/her representative will explain the nature of the study, including the risks and benefits, to the subject or their LAR (an individual or juridical or other body authorised under applicable law to consent, on behalf of a prospective subject, to the subject's participation in the clinical trial) and answer all questions regarding the study.

- Subjects must be informed that their participation is voluntary. Subjects or their parent(s)/LAR will be required to sign a statement of informed consent that meets the requirements of 21 CFR 50 (Protection of Human Subjects), local regulations, ICH guidelines, privacy and data protection requirements, where applicable, and the IEC or study centre.
- The medical record must include a statement that written informed consent was obtained before the subject was enrolled in the study and the date the written consent was obtained. The authorised person obtaining the informed consent must also sign the ICF.
- Subjects must be re-consented to the most current version of the ICF(s) during their participation in the study.
- A copy of the ICF(s) must be provided to the subject or their LAR.

Subjects who are rescreened are required to sign a new ICF.

Data Protection

In this trial processing of personal data will be carried out on behalf of the Sponsor by the CRO/the data processor, governed by a contract and strictly according and subject to the General Data Protection Regulation (GDPR) and any applicable data protection rules and regulations. As such, the Sponsor will treat data according to personal data Regulation (EU) 2016/679, and any other applicable national and international regulation. The Sponsor and the CRO/data processor will implement appropriate technical and organisational measures to ensure a level of security appropriate to the risk, taking into account the state of the art, the costs of implementation and the nature, scope, context and purposes of processing as well as the risk of varying likelihood and severity for the rights and freedoms of natural persons. Quality control will occur at each stage of data handling to ensure that all data are reliable and have been processed correctly. The Sponsor will ensure oversight of any trial-related duties and functions carried out on its behalf, including trial-related duties and functions that are subcontracted to another party by the CRO.

- All information generated in this trial is considered highly confidential and must not be disclosed to any person or entity not directly involved with the trial unless prior written consent is gained from the Sponsor. However, authorized regulatory officials, IEC personnel, the Sponsor and its authorised representatives are allowed full access to the records. All personal details will be treated as confidential by the Investigator and staff at the CRO. Prior to the processing, the Sponsor will perform an assessment of the impact of the envisaged processing operations on the protection of personal data (according to Article 35 of the GDPR). In the event of a data breach being identified, the Sponsor commits to notifying the relevant data protection supervisory authority and the individuals affected.

- Subjects and/or his/her LAR will be assigned a unique identifier by the Sponsor. Any subject records or datasets that are transferred to the Sponsor will contain the identifier only; subject names or any information which would make the subject identifiable will not be transferred. All personal identifiers according to applicable regulations (e.g., name, phone number) must be redacted permanently by the site personnel and replaced with the subject's unique identification number in all records and data before transfer to the Sponsor (or designee).
- The subject and/or his/her LAR must be informed that his/her personal study-related data will be used by the Sponsor in accordance with local data protection law. The level of disclosure must also be explained to the subject and/or his/her LAR who will be required to give consent for their data to be used as described in the informed consent.
- The subject and/or his/her LAR must be informed that his/her medical records may be examined by Clinical Quality Assurance auditors or other authorised personnel appointed by the Sponsor, by appropriate IEC members, and by inspectors from regulatory authorities.

Committees Structure

Data Safety Monitoring Board

Subject safety will be monitored by the DSMB during the study. Details for composition of the DSMB will be included in the DSMB charter.

All safety data collected will be summarised and reviewed by the DSMB for agreement of next steps.

In particular, data will be reviewed by the Sponsor for identification of the events that would potentially contribute to a requirement to pause/stop the study.

Enrolment will be paused during the first and third DSMB reviews. If a pausing/stopping rule is met, a decision will be made, based on the review, as to whether enrolment in the study will be allowed to resume.

Data Quality Assurance

All subject data relating to the study will be recorded on eCRFs unless transmitted to the Sponsor or designee electronically (e.g., laboratory data). The Investigator is responsible for verifying that data entries are accurate and correct by electronically signing the eCRF.

Guidance on completion of eCRFs will be provided in the CRF completion guidelines.

The Investigator must permit study-related monitoring, audits, IEC review, and regulatory agency inspections and provide direct access to source data documents.

Monitoring details describing strategy, including definition of study critical data items and processes (e.g., risk-based initiatives in operations and quality such as risk management and mitigation strategies and analytical risk-based monitoring), methods, responsibilities, and requirements, including handling of noncompliance issues and monitoring techniques (central, remote, or on-site monitoring) are provided in the monitoring plan.

The Sponsor or designee is responsible for the data management of this study, including quality checking of the data.

The Sponsor assumes accountability for actions delegated to other individuals (e.g., CROs).

Records and documents, including signed ICFs, pertaining to the conduct of this study must be retained by the Investigator for 25 years after study completion unless local regulations or institutional policies require a longer retention period. No records may be destroyed during the retention period without the written approval of the Sponsor. No records may be transferred to another location or party without written notification to the Sponsor.

Source Documents

- Source documents provide evidence for the existence of the subject and substantiate the integrity of the data collected. Source documents are filed at the Investigator's site.
- Data entered in the eCRF that are transcribed from source documents must be consistent with the source documents or the discrepancies must be explained. The Investigator may need to request previous medical records or transfer records, depending on the study. Also, current medical records must be available.
- The Investigator must maintain accurate documentation (source data) that supports the information entered in the eCRF.
- Study monitors will perform ongoing source data verification to confirm that data entered into the eCRF by authorised site personnel are accurate, complete, and verifiable from source documents; that the safety and rights of subjects are being protected; and that the study is being conducted in accordance with the currently approved CSP and any other study agreements, ICH GCP, and all applicable regulatory requirements.

Publication Policy

- The Sponsor will determine the identity of the Co-ordinating Investigator for the study who will review and sign off the clinical study report. This decision will be based on involvement in the study including, but not limited to, study design, subject recruitment and interpretation of study data.
- Clinical studies will be registered in public databases and summary results released / disseminated via publicly available clinical study databases according to the Sponsor's standard operating procedures and local requirements. As a general rule, both Phase 1 Healthy Volunteer studies and studies using a medicinal product in the normal course of medical practice (for example Non-Interventional Studies and Post Marketing Surveillance studies), are excluded from the above public registration and reporting requirements. If such studies do require public registration and/or reporting, this will be undertaken according to local requirements.
- The Sponsor registers clinical studies and posts the summary results as follows:
 - For clinical studies carried out exclusively within the European Union, through the EU Clinical Trial Register (EudraCT) www.clinicaltrialsregister.eu;

- Following the end of the clinical study, the summary results should be made publicly available according to accepted timelines and requirements, usually within 12 months of study completion. Special note should be taken to ensure timelines for the release of paediatric study results are met, which may be 6 months from study completion.
- For multi-site studies, it is mandatory that the first publication be based on data obtained from all analysed subjects; therefore, Investigators participating in multi-site studies must not present data gathered individually or by a subgroup of sites prior to the full, initial publication, unless this has been agreed to by all other Investigators and the Sponsor. Publication of clinical study results may include the presentation of such work at national and international congresses, symposia, professional meetings, peer-reviewed journals, and via other appropriate channels. Named authors and contributors to such publications shall be determined by the Sponsor in accordance with both the Company Publication Policy (which can be found at: <http://www.mundipharma-rd.eu/research-areas/publications.html>) and the generally accepted criteria for authorship as outlined by the International Committee of Medical Journal Editors authorship guidelines. The data associated with any publication will be and shall remain the sole property of the Sponsor; the copyright of the document may be transferred to the scientific peer-reviewed journal prior to and as part of the publication process, as appropriate.
- Subject to the paragraph above, the site may publish or present the results of the clinical study subject to the protection of the Sponsor or its nominee(s) intellectual property rights, know-how, and its proprietary information. The Sponsor must be furnished with a copy of any proposed publication or presentation at least 60 days prior to submission for review and comment. Upon notice by the Sponsor, however, that the Sponsor intends to secure its intellectual property rights (for example, file a patent application relating to the study) or that Sponsor requires for its know-how or proprietary information to be removed prior to such publication, such publication may be delayed for a further 6 months or until its intellectual property rights have been secured, whichever is the later. The site further agrees that Sponsor's reasonable comments in relation to the proposed publication will be incorporated into the publication.

